8.4 Subject related information

8.4.1 Demography

The following demographic data will be obtained by the Investigator and recorded:

- Date of birth (if not permitted according to local laws the year of birth will be collected)
- Age at screening
- Age at randomisation
- Ethnicity (if permitted according to local laws)
- Race (if permitted according to local laws)
- Sex

The Investigator must document whether females are of non-childbearing potential in the Subject medical record and eCRF.

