2.4 Secondary endpoints

2.4.1 Supportive secondary endpoints

For all supportive secondary endpoints, meal-time fast-acting insulin aspart will be compared to meal-time NovoRapid®, and post-meal fast-acting insulin aspart will be compared to meal-time NovoRapid®. Change from baseline refers to the change from randomisation to 26 weeks after randomisation.

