Furthermore summary tables based on system organ class and preferred term are made for

- All TEAEs
- Serious TEAEs
- Possibly or probably related TEAEs
- Severe TEAEs
- TEAEs with preferred term that are experienced by at least 5% of the Subjects in any treatment arm or by at least 5% of all Subjects

For AEs where additional information is recorded, this will be listed.

AEs occurring during the run-in period are considered non treatment emergent and will be summarised separately.

- Number of treatment emergent injection site reactions

Injection site reactions occurring during the trial, related to either basal and/or bolus insulin will be summarised and listed. No formal statistical analysis will be made.

- Change from baseline in clinical evaluations
 - Physical examination (head, ears, eyes, nose, throat, neck, respiratory system, cardiovascular system, gastrointestinal system incl. mouth, musculoskeletal system, central and peripheral nervous system, skin, Tanner stage)
The physical examination parameters, and their change from baseline, will be summarised descriptively in shift tables. All findings will be listed.
 - Vital signs (blood pressure, pulse)

Vital signs include diastolic blood pressure, systolic blood pressure and pulse. The measurements and their change from baseline will be summarised descriptively.

- Change from baseline in body weight, height, body mass index (BMI) and SD-score of body weight and BMI (z-score)

SD-scores are defined to be able to normalise the body weight in the various age groups. To estimate the growth of children, standardised weight is calculated for each year of age and for each sex. Thus, a child with a weight equal to the mean value for its age and sex has an SD score of 0, while a child with a weight 2 SDs above the mean value for its age and sex has an SD score of +2. The SD scores are derived from the age and sex of the Subjects and the body weight together with growth curves defined for a reference population. SD scores for BMI will be determined in a similar way as SD scores for weight by use of a suitable reference population based on age and sex. For all countries except Japan and India the reference values for the US will be used. The SD scores for Japanese Subjects will be based on country specific references whereas SD scores for Indian Subjects below 5 years of age will be based on World Health Organization (WHO) references and otherwise country specific references.

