The measurements and their change from baseline will be summarised descriptively. In addition, the endpoints will be analysed separately using a statistical model using multiple imputation similar to 1) including treatment, region and age group as factors and the corresponding baseline measurement as covariate. The analyses will be based on the SAS and the on treatment observation period.

- Change from baseline in laboratory assessments

- Haematology (haemoglobin, haematocrit, erythrocytes, thrombocytes, and leucocytes)
- Biochemistry (creatinine, , alanine aminotransferase (ALT), aspartate aminotransferase (AST), alkaline phosphatase (AP), sodium, potassium, albumin, and total bilirubin)
- Lipid profile (total cholesterol, high density lipoprotein (HDL), low density lipoproteins (LDL))

Individual laboratory values will be compared to their relevant reference range (when existing) and flagged as being below or above the range. The measurements and their change from baseline will be summarised descriptively. Change from baseline will be summarised descriptively using both the actual values and the low/normal/high categorisation in shift tables.

Lipid endpoints (LDL, HDL, and total cholesterol) will be log-transformed and analysed separately using a statistical model using multiple imputation similar to 1) including treatment, region and strata as factors and the corresponding log-transformed baseline measurement as covariate. The

analyses will be based the FAS and the in trial observation period and repeated using the on treatment observation period. The treatment difference and associated 95% confidence intervals will be back-transformed providing results in terms of ratios of geometric means on the original scale. NovoRapid® will be used as reference.

- Change from baseline in anti-insulin aspart (specific and cross-reacting with human insulin) antibody development

The measurements and their change from baseline will be summarised descriptively. The correlation to other relevant variables such as insulin dose and HbA_{1c} are illustrated using graphs.

3 Changes to the statistical analyses planned in the protocol

Minor editorial corrections have been made throughout the document.

General considerations

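### An Indian child who turns 5 on trial can have an SD-score change computed across two growth references, and the body-size models replace the strata with coarse age bands without declaring it

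*SAP*

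**What the plan says.** **How the score is built.** SAP section 2.4.1.2 introduces the SD score by saying that "standardised weight is calculated for each year of age and for each sex", and illustrates it with a child at the mean and a child two SDs above it. It then gives the derivation, which rests on a reference population: "The SD scores are derived from the age and sex of the Subjects and the body weight together with growth curves defined for a reference". Protocol section 17.4.1.2 has the same two elements. Neither document says whether age is in whole years or exact, or whether the week-26 score uses age at that visit.

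**Which reference applies.** The SAP states: "For all countries except Japan and India the reference values for the US will be used". For Japan: "The SD scores for Japanese Subjects will be based on country specific references". For India: "SD scores for Indian Subjects below 5 years of age will be based on World Health Organization (WHO) references and otherwise country specific references". The protocol used each country's own reference, with US values where none was accessible, and had no switch at age 5.

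**What the change covers.** SAP section 2.4.1: "Change from baseline refers to the change from randomisation to 26 weeks after randomisation".

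**The model.** The SAP analyses raw weight, height and BMI and the two SD scores with a multiple-imputation model "including treatment, region and age group as factors" and the baseline value as covariate. The protocol's model for the same endpoints had treatment, region and strata. The SAP defines age group as 1 to under 6, 6 to under 12 and 12 to under 18 years; the strata split the youngest band at 3 years.

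**Age data.** Protocol section 8.4.1 collects date of birth, but "if not permitted according to local laws the year of birth will be collected". It also collects age at screening and age at randomisation.

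**The concern.** A change in SD score is interpretable only if both scores come from the same yardstick, read at the child's age on each occasion. The Indian rule breaks the first condition for any child who passes age 5 between the two visits. The description of the score leaves the second condition unstated. If reference values were held constant within each year of age, a child with a birthday in follow-up would be compared with a norm a full year older, and a child without one with an unchanged norm.

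The model raises a different question. SAP section 1.2 says that changes to the protocol's statistics, with reasons, are described in section 3, and this change of factor is not there. In the raw weight, height and BMI models, children six years apart in age can share one age-group effect, and sex is absent, although growth over 26 weeks depends on both.

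At stake are the growth-adjusted safety endpoints of a paediatric insulin trial: the cleanliness of individual and small-subgroup changes, the precision of the body-size comparisons, and the traceability of the plan.

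**Working it through.** The plan gives no figure on this point, so there is none to reproduce.

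**1. The age-5 switch.** For a child under 5 at baseline and 5 or over at week 26, the rule as written gives

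change = z(national, week 26) − z(WHO, baseline) = [z(WHO, week 26) − z(WHO, baseline)] + [z(national, week 26) − z(WHO, week 26)].

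The second bracket is the difference between two references for the same child on the same day. It is not growth.

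How many children are affected:
- Follow-up: T = 26 × 7 / 365.25 = 0.498 year.
- From the documents: the aim of at least 20 subjects under 6 per arm (Protocol 6.1) and 250 per arm (SAP 2.1).
- Assumed, because the documents do not give them: ages uniform within the range, Indian share 5% to 20%, jump between references 0.2 to 1.0 SD.

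| Age assumption | Crossing age 5 per arm, all countries | Indian children crossing per arm | Shift in arm mean (n = 250) |
|---|---|---|---|
| 20 per arm uniform on 1 to <6 | 20 × 0.498/5 = 2.0 | 0.1 to 0.4 | 0.0001 to 0.0016 SD |
| 250 per arm uniform on 1 to <18 | 250 × 0.498/17 = 7.3 | 0.4 to 1.5 | at most about 0.006 SD |

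The shift is (number crossing × jump)/250; for example 0.4 × 1.0/250 = 0.0016. In an under-6 subgroup of 20 per arm it is up to 0.4 × 1.0/20 = 0.02 SD. Assignment is random and stratified by age, so the expected shift is the same in every arm.

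**2. Whole-year steps, if the literal reading were programmed.** Let r be the yearly rise of the reference mean in SD units (assumed 0.3 to 1.0; not in the documents). For a child growing exactly along the reference, the spurious change is:
- no birthday in follow-up (probability 1 − T = 0.502): r × 0.498;
- birthday in follow-up (probability T = 0.498): r × (0.498 − 1) = −0.502 r.

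Mean = 0.502 × 0.498 r − 0.498 × 0.502 r = 0. SD = r × √(0.498 × 0.502) = 0.50 r, which is 0.15 at r = 0.3, 0.25 at r = 0.5 and 0.50 at r = 1.0.

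The standard error of the treatment difference would be multiplied by √(s² + 0.25r²)/s, where s is the true SD of change (assumed 0.3 to 0.5). This gives 1.04 to 1.12 at r = 0.3, 1.12 to 1.30 at r = 0.5 and 1.41 to 1.94 at r = 1.0. Both r and s are assumed, and at exact age the component is zero. The width of this range shows that the size is unknown; it is not an estimate of loss.

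**3. Model factors, side by side.**

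| Place | Age term |
|---|---|
| Protocol 17.4.1.2, body measurements | strata (four bands) |
| SAP 2.4.1.2, body measurements | age group (three bands) |
| SAP 2.4.1.2, lipids | strata |
| SAP 3, where age group is declared | selected tables and figures only |
| SAP 3, entry for body measurements | analysis set, observation period and references; age term not mentioned |

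Section 3 justifies the merged youngest band by the small number of subjects under 3, but only for presentation. The primary HbA1c model keeps the strata.

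**The case against.** The sentence about each year of age explains what an SD score is. The derivation that follows relies on growth curves, which one would naturally read at the child's actual age, and nothing says that age is truncated. This stands: the text permits whole-year steps but does not prescribe them.

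A reader might infer that the reference changes for most children. It does not. Only Indian children passing age 5 can change reference population; Japan has one reference and all other countries use US values. Comparing a child with an older norm at a later visit is how an SD score is meant to work.

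A reader might also infer that overall mean changes are distorted. The arithmetic is against this: with evenly spread birthdays the whole-year error averages zero, and the age-5 contribution to an arm mean is at most a few thousandths of an SD.

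The Indian rule could be read as classifying each child once, at baseline. That would remove the problem, but the SAP does not say so.

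On year of birth, age at randomisation is also collected, so fearing that only whole-year age would be available goes beyond the documents.

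On the model, baseline value already carries some age information, and merging two small strata is reasonable. Adding age and sex is a gain in efficiency and does not repair a bias. Neither answer accounts for the missing declaration.

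**Conclusion.** The point holds in a limited form.

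- **Reference switch.** As written, the Indian rule gives a change across two references for a child who turns 5 on trial. The expected number is well below two per arm under the stated assumptions, and the treatment difference is not biased in expectation. What suffers is those children's own values and, slightly, any under-6 summary.
- **Age precision.** This is a missing detail. If whole-year values were used, SD-score changes would carry zero-mean noise. Its size depends on quantities the documents do not give, so no interval-widening percentage should be quoted as a finding.
- **Model.** The move from strata to age group is a verifiable, undeclared departure from the protocol. Leaving exact age and sex out of the raw weight, height and BMI models forgoes precision, because the two older bands each span six years. SD scores are already standardised for age and sex, so this part does not apply to them.

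These are supportive secondary safety endpoints, not among those marked as key, and outside the confirmatory hierarchy. The HbA1c tests and the sample size are untouched, and raw body measurements are unaffected by the choice of reference.

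**What to change.** In SAP section 2.4.1.2:

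1. Assign each child one growth reference at baseline and use it at both visits. A child just under 5 at baseline will be at most about 5 + 0.498 = 5.5 years at week 26, so confirm that the chosen reference reaches that age. If it does not, add a sensitivity analysis without children who pass age 5.
2. State that the curves are read at exact age at each measurement date. Where birth date is unavailable, use age at randomisation plus elapsed time. Even if that field is held in whole years, the same offset then applies at both visits and no birthday step arises.
3. Add age at randomisation and sex as covariates in the raw weight, height and BMI models.
4. Restore the randomisation strata in the body-size models, or declare and justify age group in section 3.

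The cost is a few sentences and minor programming. Age at randomisation and sex are already collected, and no new data, visits or subjects are needed. With items 1 and 2 in place, both the reference-switch and whole-year components are zero.
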